#### 1.3.3 Clinical outcomes from PBT in adult glioma patients

There is very limited published evidence concerning outcomes for patients with LGG/ ODG treated with PBT. Shih, Sherman and Tabrizi reported a series of prospective single arm studies which included 20 adult LGG patients (not molecularly defined) treated with PBT (Shih et al. 2015; Sherman et al. 2016; Tabrizi et al. 2019). After median follow-up of 5.1 years, NCF and HRQoL remained stable (Shih et al. 2015; Sherman et al. 2016). New endocrine dysfunction developed in 6 patients (Shih et al. 2015). A recent update, after median follow-up of 6.8 years, confirmed no overall decline in NCF, although 5 patients who reported cognitive/ mood symptoms around the time of PBT also showed progressively worse NCF on follow-up (Tabrizi et al. 2019). Toxicities occurring at >2 years were mainly neurological or endocrine. HRQoL remained stable or improved over time (Tabrizi et al. 2019). Additional small (n=19-71) non-randomised cohort studies have evaluated PBT in adult ODG patients, mainly with short follow-up and thus a focus on acute toxicities (Hauswald et al. 2012; Maguilan et al. 2014; Wilkinson et al. 2016; Sas-Korczynska et al. 2017: Nystrom et al. 2018: Nagaraja et al. 2019), which appear acceptable. These mainly consist of mild to moderate alopecia, dermatitis, fatigue and headache. In summary, the majority of published studies concerning PBT in OGD are small, single centre and nonrandomised with limited follow up. RCTs are therefore urgently needed to determine if the dosimetric benefits of PBT, in comparison to photon RT, translate into clinical benefit (Thurin et al. 2018).

#### 1.4 On-going studies

The APPROACH trial will contribute to global efforts to define the place of PBT in glioma patients alongside two non-UK randomised studies, described below. These compare PBT with photon RT in overlapping, but non-identical, patient populations. Outcomes from APPROACH, focusing specifically on the ODG population, using the same primary endpoints, will contribute to a high impact, practice changing evidence base.

NRG-BN005 is an American phase II RCT of PBT vs. photon RT followed by adjuvant temozolomide (TMZ) chemotherapy in 120 grade II/III IDH mutant adult glioma patients (NCT03180502), (NRG Oncology 2017). The primary endpoint is NCF, with initial analysis at 2 years and follow-up to 10 years. The estimated study completion date is January 2030. The study includes worse prognosis patients (i.e. non-1p19g co-deleted), in whom TMZ chemotherapy may be more appropriate. For ODG patients, however, the evidence supports the use of adjuvant PCV, as specified in UK protocols (van den Bent et al. 2013; Buckner et al. 2016; National Institute for Health and Care Excellence 2018). TMZ and PCV may impact NCD differently but this is unknown. Given the differences in population and chemotherapy. the United States (US) results will not directly translate to the UK. We are, however, working with the US team to align assessments and increase the evidence base across molecular pathologies and treatment regimes. We are using the same neurocognitive tests and evaluating the same treatment effect for the primary endpoint. Through on-going collaboration, we aim to perform a future individual participant data meta-analysis (separately funded) and also have the potential to pool dosimetric and imaging data to further strengthen our mechanistic work. A German 80-patient trial of PBT vs. photons is also ongoing (DRKS00015160) for adult patients with IDH mutant grade II and III gliomas

(GliProPh 2018). The primary endpoint is NCF at 3 years, with annual neurocognitive testing for 6 years. As with the US trial, a higher risk group of patients are included in the German trial, meaning conclusions will not be directly applicable to the ODG patient group.

Single arm PBT studies are also ongoing:

• A Dutch single-arm PBT observational trial is recruiting 79 grade II/III IDH mutant adult glioma patients. Primary endpoints are NCF and toxicity over 4 years (NTR7993) (Erasmus MC 2019).

• A US single arm PBT phase II trial has recently recruited 63 adult grade II/III glioma patients to assess survival and toxicity over 7 years (NCT01358058) (Massachusetts General Hospital 2011).

• A German trial (DRKS00007670) includes a variety of high- and low-grade brain tumour patients requiring high dose RT (Proto-R-Hirn 2014). All patients receive PBT. The primary endpoint is grade 2+ late toxicity after 2 years.

• A phase I trial of Proton/Carbon-ion RT in combination with TMZ in adult patients with high-grade glioma is ongoing in Shanghai (Shanghai Proton and Heavy Ion Center 2017).

Single arm studies cannot provide the urgently required randomised evidence regarding the benefit of PBT over photon RT. Non-randomised evidence, however, could be included within the future planned individual participant data meta-analysis.

#### 1.5 Patient and public involvement (PPI):

We have actively worked with, and iteratively developed this trial based on constructive feedback from, ODG patients, caregivers and our PPI co-applicant.

A focus group was held in November 2018 with 15 ODG patients and caregivers from Leeds and Manchester to discuss the potential benefits of PBT (Powell et al. 2020). Attendees strongly endorsed the trial proposal and opportunity to access PBT within an RCT. The group were adamant that randomisation should be 1:1 between PBT and photon RT to demonstrate clinician equipoise between modalities and so this has been adopted. Patients disliked some traditional terminology such as 'trial' and 'neurocognitive tests' and preferred research study' and 'neurocognitive assessments', which will be incorporated into all patientfacing material. Patients and caregivers expressed the need for careful consideration of issues around travel and accommodation during PBT away from home. The trial will therefore endeavour to ensure that appropriate support is provided to ensure that all patients who wish to participate are able to do so. The group also highlighted that the experience of a caregiver was different to that of a patient, hence caregiver wellbeing questionnaires have been included as part of the trial. Participants considered that standard HRQoL questionnaires (European Organisation for Research and Treatment of Cancer (EORTC) Quality of Life Questionnaire Core 30 (QLQ-C30) (Aaronson et al. 1993), and Brain Cancer Module (EORTC BN20), (Taphoorn et al. 2010) fail to address some important areas reflecting daily wellbeing, including issues related to fatigue and getting along with one's family. As such, additional questionnaires have been included to better cover these issues. Patients considered the proposed schedule and assessments acceptable and were willing to complete questionnaires and neurocognitive tests for "as long as is necessary" (Powell et al. 2020).

#### 1.5.1 Other patient groups:

The results of this trial, performed within a young, uniformly good prognosis subgroup of brain tumour patients, will inform relevant questions in a wider group of adults with other good prognosis brain tumours where RT is frequently used. Although the specific impact of treatment may differ due to different dosimetry and target volumes, data from APPROACH will help to frame the critical issues in, for example, meningioma (~1430 cases in England per annum, respectively (Maile *et al.* 2016).

#### 1.6 Mechanistic evaluation: neuroanatomical target theory

Neuroanatomical target theory investigates potential mechanisms of radiation-induced neurocognitive dysfunction through examination of the RT dose received by different regions within the brain (Peiffer et al. 2013). The mechanistic hypothesis within APPROACH is that there are definable dose-response relationships for specific brain regions in adults, which impact on NCF. This hypothesis is supported by a significant literature in adult patients undergoing RT for a variety of cancers, including nasopharyngeal carcinoma in whom the temporal lobes are treated to high doses. Here, dose-response relationships have been defined for specific brain substructures (Lam et al. 2003; Lv et al. 2019; Yang et al. 2019). In adults with brain tumours, relationships between RT dose to the hippocampus and memory impairment have been most widely examined with a view to hippocampal RT dose sparing in an effort to preserve memory (Gondi et al. 2013; Brown et al. 2020). Neurocognition is, however, considerably more complex than hippocampal dependent memory function: individual aspects of neurocognition rely on interconnecting networks throughout the brain and the dose response relationships for the majority of relevant regions and networks remains undefined (Greene-Schloesser et al. 2012; Peiffer et al. 2013; Hart et al. 2019; Duffau 2020). For example, working memory requires an extensive network of communication between the hippocampus, amygdala, cerebellum and prefrontal cortex; this whole network has yet to be investigated. Indeed, a hippocampal normal tissue complication probability (NTCP) model predicting memory impairment has not been validated in LGG patients (Jaspers et al. 2019), necessitating a shift in attention to other brain regions/ networks involved in neurocognitive functioning (Duffau 2020).

In regard to existing data on regional dose-neurocognitive dysfunction response relationships in adults (other than the hippocampus), series are mainly small and often perform neurocognitive testing at a single, yet variable time point post-RT, making conclusions less reliable (Brummelman *et al.* 2012; Peiffer *et al.* 2013; Tabrizi *et al.* 2019; Haldbo-Classen *et al.* 2020). Furthermore, data tends to focus on specific anatomical substructures rather than allow for structural network connectivity.

Lesion Symptom Mapping (LSM) (also known as Voxel-based Lesion Symptom Mapping: VLSM) is a well-established method to relate brain location to brain function (Bates *et al.* 2003), that has been widely used in the setting of stroke and trauma. Applying LSM to map normal tissue RT dose to cognitive deficits is highly novel. By focusing on individual voxels, which may not be specific to one anatomical substructure, this allows an unbiased assessment of anatomical network contributions to cognition, beyond a pure substructure approach. An advantage of LSM is that it can be performed using the standard Magnetic Resonance Imaging (MRI) planned within this study.

Prospective data collection with consistent time points for neurocognitive testing using a fixed test battery is required to move this field forwards (Peiffer *et al.* 2013; Duffau 2020). APPROACH provides this unique and powerful opportunity. The identification of 'at risk' regions of normal brain will facilitate sparing of these regions from RT, which is particularly applicable for PBT as it more easily facilitates sculpting of dose away from critical regions.

This will also permit identification of patients for whom PBT will provide the largest benefit (i.e. those in whom sparing cannot be achieved by photons but can with PBT). In those in whom sparing cannot be achieved due to tumour location, improved understanding of regional dose neurocognitive dysfunction relationships will allow quantification of risks of specific deficits. This will permit more informed clinician-patient discussions regarding the risks vs. benefits of treatment and facilitate targeted neurorehabilitation, aiming to manage these complications and thus maintain HRQoL.

### 2 Aims and Objectives

#### 2.1 Trial Aim

To assess whether good prognosis ODG patients treated with PBT have better NCF in comparison to those treated with standard photon RT.

#### 2.2 Primary trial objectives

A multi-staged assessment approach is proposed:

• Stage 1 (internal pilot): To confirm feasibility of recruitment in terms of patient willingness to be randomised,

• Stage 2: To assess if there is an early neurocognitive benefit of PBT on an intermediate endpoint of NCF at 2 years compared to photon RT (the earliest time point at which chronic RT-related NCD might be expected to be identified based on the existing evidence), providing sufficient evidence in favour of PBT in ODG patients to warrant an early practice-defining decision. Regardless of the outcome at stage 2, trial follow-up will continue to 5 years to provide essential data about the long-term individual and societal impact of PBT (Lawrie *et al.* 2019),

• Stage 3: To undertake an interim futility assessment on the primary endpoint of 5year NCF when ≥50% patients have reached 5-year follow-up, to ensure there is sufficient evidence to warrant continuation of follow-up to 5 years for all patients,

• Stage 4: To assess if there is sufficient evidence of treatment benefit based on 5year NCF when compared to photon RT to warrant the use of PBT in patients with ODG.

#### 2.3 Secondary trial objectives

To evaluate the impact of PBT in comparison to photon treatment for:

- Additional NCF outcomes
- HRQoL
- Endocrinopathy
- Treatment compliance
- Work & economic impact
- Caregiver distress
- Early and late toxicity
- Radiological response rates
- Progression-free survival
- Overall survival

See section 11 Endpoints for full definitions of the primary and secondary trial endpoints.

#### 2.4 Mechanistic component

#### 2.4.1 Mechanistic Aim

To improve understanding of RT dose-neurocognitive dysfunction relationships to facilitate future sparing of eloquent brain areas, either through changes in RT planning priorities (for photon RT or PBT) or choice of RT treatment technique (i.e., Photon RT vs. PBT).

#### 2.4.2 Mechanistic Hypothesis

The mechanistic hypothesis is defined as:

There are definable dose-neurocognitive dysfunction relationships for specific brain regions in adults, which impact on NCF.

#### 2.4.3 Mechanistic Objectives

The mechanistic objectives are defined as:

1. To investigate the impact of RT dose to different substructures within the brain on NCF.

2. To investigate the impact of RT dose location on NCF using LSM.

A separate mechanistic analysis plan will be developed and will be reassessed throughout the duration of the trial given that the mechanistic analysis will not take place until years nine and ten of the grant. The analysis plan will incorporate any developments in the research literature in this field over time.

### 3 Trial design overview

APPROACH is a phase III UK multi-centre, open-label RCT with multi-staged assessments. The two-arm RCT of PBT vs. photon RT in patients with ODG, will assess whether good prognosis ODG patients treated with PBT have better NCF in comparison to those treated with standard photon RT. Neurocognitive function will be assessed at baseline, one month post end of RT and at each annual follow-up.

A total of 246 patients will be randomised 1:1 between PBT and photon RT, with PBT being delivered in one of the two NHS PBT centres and photon RT being delivered in the local RT centre. For those randomised to PBT, during PBT, the participant will be under the care of the clinician in the PBT centre, who will be responsible for their RT planning, prescription and delivery. For those randomised to photon RT, during photon RT, the participant will be under their radiotherapy planning, prescription and delivery. In the lead up to RT (PBT or photon RT), during adjuvant chemotherapy and during follow up, the participant will be under the care of the clinician in the local centre. Following radiotherapy, all patients will receive adjuvant PCV chemotherapy, with clinical review and chemotherapy toxicity recorded at each cycle.

Follow up will be as standard of care, with trial-specific assessments at baseline, weekly during RT and at 1, 3, 6, 12, 24, 36, 48 and 60 months post end of RT. Secondary endpoints also include additional NCF outcomes, HRQOL, endocrinopathy, treatment compliance, work and cost impact, caregivers distress, early and late toxicity, response assessment, progression free survival (PFS) and overall survival (OS).

There are four stages of assessment to ensure trial continuation is warranted throughout. Recruitment will take place in 18-25 centres over 3/2 years.

• Stage 1: (internal pilot phase) will confirm feasibility of recruitment over the first 12 months. If successful, the trial will continue to full recruitment and Stage 2 assessment.

• Stage 2: an interim analysis of NCF at 2 years as an intermediate endpoint for early signs of efficacy will be performed once all patients reach  $\geq$ 2-year follow-up. If positive there is the potential to recommend change in practice; trial follow-up will continue regardless for longer term outcomes.

• Stage 3: a further interim analysis will be performed when 50% of patients reach 5year follow-up to assess futility. If futility is concluded, follow-up may be terminated early for the remaining patients.

• Stage 4: final analysis. The primary endpoint focused on NCF at 5 years. If positive there is the potential to recommend change in practice for standard of care. All secondary endpoints will also be assessed.

Stage 1 provides an early stop if predetermined recruitment targets are not met; Stage 2 provides an early practice changing opportunity on an intermediate endpoint; and Stage 3 provides stopping rules for longer term follow-up.

#### 3.1 Setting

#### 3.1.1 Patients allocated to receive photon radiotherapy

Photon radiotherapy will be delivered daily on weekdays as an out-patient in the local RT centre. The participant will be under the care of the clinician in the local RT centre, who will be responsible for their radiotherapy planning, prescription and delivery as well as their ongoing care and follow up.

#### 3.1.2 Patients allocated to receive proton beam therapy (PBT)

PBT will be delivered daily on weekdays as an out-patient in one of the two UK NHS PBT centres. The PBT centre that will be allocated for treatment will depend on participant location and centre availability.

During PBT, the participant will be under the care of the clinician in the PBT centre, who will be responsible for their radiotherapy planning, prescription and delivery. In the lead up to PBT, after completion of PBT, during adjuvant chemotherapy and during follow up, the participant will be under the care of the clinician in the local centre.

If a patient has been randomised to receive proton beam therapy, the PI or delegate must enter the patient's details on the NHS National Proton Therapy Referral Portal:

#### https://protons.protontherapyreferrals.nhs.uk/Login/Signin

Following confirmation that a patient has been appropriately referred and accepted for PBT they will be contacted by a 'key worker', who will be a named specialist nurse or radiographer from one of the NHS proton centres. The role of the key worker is to provide assistance and support to the patient throughout the treatment. The key worker will contact the patient and referring clinician to arrange for the patient and relative/ friend/ caregiver to attend for a pre-treatment single-assessment visit, which should be within around ten days of receipt of the referral through the Portal. The key worker will discuss the travel and accommodation arrangements during treatment and answer any practical questions that the patient may have. Further guidance related to the referral portal can be found in the **APPROACH Portal Referral Guidelines**.

#### 3.1.2.1 Accommodation and travel for patients allocated to receive PBT

Patients allocated to PBT will need to visit one of the two national NHS proton centres for treatment planning and the treatment itself.

The proton centres are located at:

- The Christie NHS Foundation Trust in Manchester,
- University College London Hospitals NHS Foundation Trust in London.

Patients do not have to stay in the provided accommodation and if they would prefer to return home every day following their treatment, they can do so. The NHS will provide accommodation for the pre-assessment visit and duration of radiotherapy for one patient plus one partner or caregiver. The accommodation arrangements will be made by the key worker from the PBT centre and only accommodation suggested by the PBT centre will be

funded by the NHS. Further details about the accommodation will be provided to the patient once acceptance to either PBT centre has been made.

Patients will need to make their own travel arrangements. The assigned key worker should discuss the travel arrangements with the patient and answer any questions that the patient may have. The trial will not provide any reimbursement for travel provisions, though eligible participants may be reimbursed for patient travel expenses under the 'Healthcare Travel cost scheme'. More information can be found at: https://www.nhs.uk/nhs-services/help-with-health-costs/healthcare-travel-costs-scheme-htcs/

#### 3.2 Study population

Adults (≥25 years) with ODG (PBT is already commissioned for children and young adults <25 years with ODG).

### 4 Eligibility

Patients meeting all of the inclusion criteria and none of the exclusion criteria will be considered for participation in the trial. Eligibility waivers to any of the inclusion and exclusion criteria are not permitted.

#### 4.1 Inclusion criteria

- Histologically proven diagnosis of ODG with 1p19q co-deletion and IDH mutation.
- Randomisation must be performed within 28 days of the MRI that leads to the decision that RT is required at that point in time. Outside of 28 days, an updated MRI is required to serve as a contemporaneous baseline scan to assess response to further treatment.
- Karnofsky Performance Status (KPS) ≥70%.
- Adequate wound healing and recovery if recent surgery.
- Suitable to complete baseline neurocognitive testing (No access to translated tests, only English versions available).
- Patients of childbearing potential should be asked to confirm that they are not pregnant to confirm trial eligibility. Formal Pregnancy testing should be performed if there is any doubt as to pregnancy status or if felt appropriate, including in circumstances such as irregular periods, unprotected sexual intercourse since the last menstrual period, missed contraceptive pill or antibiotics during the last menstrual cycle or failure of barrier contraception. See 4.3 Birth control: contraception and pregnancy testing for further details.
- Fertile participants, born male, must agree to practice methods of contraception that are considered medically acceptable for the duration of RT, adjuvant chemotherapy and for 6 months post-end of treatment if sexually active with a person of child-bearing potential. See section 4.3 Birth control: contraception and pregnancy testing for further details.
- Able to swallow oral medication.
- Able to provide study-specific informed consent.
- Age 25 or over at the point of starting RT treatment.
- No known haematological, renal or hepatic impairments making PCV chemotherapy inappropriate

#### 4.2 Exclusion criteria

- Pregnancy (positive pregnancy test) or lactating.
- Prior cranial or head and neck RT.
- Any previous chemotherapy for the treatment of ODG.
- Co-morbid neurodegenerative diseases that influence NCF.
- Contra-indication to MRI scan or gadolinium.
- Severe active co-morbidity making patient unsuitable for radiotherapy and/ or adjuvant chemotherapy (e.g., uncontrolled diabetes, uncontrolled hypertension)
- Leptomeningeal disease.
- Spinal or infratentorial disease.
- Another currently active malignancy or another malignancy within the last 3 years.
- Any contra-indication to Procarbazine, Vincristine or Lomustine (see section 8.2.1 Chemotherapy contraindications for further information) including: coeliac disease; and the rare hereditary problems of galactose intolerance, total lactase deficiency or glucosegalactose malabsorption.
- Any recognised genetic syndrome causing sensitivity to radiotherapy.

• Patient unwilling/ unable to attend for follow up in the local radiotherapy centre.

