# 7.2 Recruitment and informed consent

Patients will be identified through clinic lists and multidisciplinary team meeting (MDTs) and approached for possible recruitment in out-patient clinics. Suitability for inclusion into APPROACH will be assessed according to the eligibility criteria for the trial. A verbal explanation of the trial and the appropriate Patient Information Sheet (PIS) will be provided by the attending medical staff (and/or the trial Clinical Research Nurse) for the patient to consider. This will include detailed information about the rationale, design and personal implications of the trial. Before a patient can enter the trial (if they are of child-bearing potential) they will be asked to read through an APPROACH specific shortened pregnancy eligibility screening PIS and then asked to sign this Informed Consent Form (ICF), if they are willing to be pregnancy screened in order to take part in the APPROACH trial. A patient of child-bearing potential cannot enter the trial unless they have confirmed that they are not pregnant with their doctor/treatment team. If there is any doubt, the pregnancy screening should be carried out prior to patient consent to the trial, but the patient should be allowed to take as much time as needed to decide about trial participation. If a patient of child-bearing potential agrees to be screened for pregnancy prior to consent, they can be provided with the main PIS/ICF and, following information provision, patients will have as long as they need to consider participation, normally a minimum of 24 hours, and will be given the opportunity to discuss the trial with their family and healthcare professionals before they are asked whether they would be willing to take part in the trial.

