# **13 Statistical Analysis**

#### 13.1 General considerations

Statistical analysis for the main trial endpoints is the responsibility of the CTRU Statisticians. The analysis detailed below provides an overview of the analyses to be performed for the main trial. A separate and fully detailed statistical analysis plan (SAP) will be written in accordance with CTRU SOPs, prior to any analyses being performed.

Analysis of the primary and secondary endpoints will be performed on an intention-to-treat (ITT) basis, unless specified otherwise within the SAP.

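### Eligibility checks attendance only for local follow-up, while PBT referral and acceptance follow randomisation in one arm, so a patient who cannot take up PBT can be randomised and stays in the ITT comparison

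*Protocol*

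**What the plan says.** - **Eligibility.** The last item in Protocol 4.2 excludes a "Patient unwilling/ unable to attend for follow up in the local radiotherapy centre". No other item in 4.1 or 4.2 deals with attendance, and none mentions ability to travel to a PBT centre or acceptance for PBT. Section 4 permits no waivers.
- **PBT pathway.** Section 3.1.2 starts it after allocation: "If a patient has been randomised to receive proton beam therapy, the PI or delegate must enter the patient's details" on the national referral portal. The same section continues: "Following confirmation that a patient has been appropriately referred and accepted for PBT they will be contacted by a 'key worker". The pre-treatment visit and the discussion of travel and accommodation come next. Section 3.1.2.1 gives further accommodation details "once acceptance to either PBT centre has been made". Photon patients have no matching step.
- **Travel.** Section 1.5 reports that "Patients and caregivers expressed the need for careful consideration of issues around travel and accommodation during PBT away from home". Section 3.1.2.1 states that "The trial will not provide any reimbursement for travel provisions", although eligible participants may claim from a national scheme. The NHS provides accommodation for the patient and one companion.
- **Consent.** Section 7.2 requires an explanation of the trial before randomisation: "This will include detailed information about the rationale, design and personal implications of the trial".
- **Analysis.** Section 13.1: "Analysis of the primary and secondary endpoints will be performed on an intention-to-treat (ITT) basis", unless the SAP specifies otherwise. Section 7.2 keeps patients who are given alternative treatment in follow-up and analysis.
- **Sample size.** Section 12.1 allows for 30% loss to follow-up and nothing else.

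**The concern.** The protocol does treat attendance as an eligibility matter, but only for follow-up visits close to home. The heavier demand, a full weekday course in Manchester or London, falls on one arm and is not tested. A patient who can attend locally but cannot spend that time at a proton centre meets every listed criterion. If such a patient is allocated photons, nothing is lost. If allocated PBT, the obstacle appears only after randomisation.

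A patient then treated with photons is analysed in the PBT arm and pulls the 5-year difference in neurocognitive function towards zero. A patient who instead leaves the trial adds missing data in one arm. Movement the other way is unlikely, since section 1.3 says that UK PBT is commissioned only for very limited indications. This route is therefore one-sided, and part of it could be closed before randomisation. The pilot decision in section 13.3 rests only on the number recruited, so low PBT uptake would not trigger review at that stage.

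**Working it through.** **Inputs**

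- Difference 0.5, SD 1, two-sided 5%, 90% power, 86 evaluable per arm, 30% loss, 123 per arm (section 12.1).
- Alpha 0.04 at 5 years if the 2-year result is not significant, stated power about 89%. Alpha 0.01 at 2 years with 10% dropout, stated power about 87% (section 13.3).
- Share c of the PBT arm that does not receive PBT: **not given in the protocol**, so it is varied here.

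**Step 1: reproduce the plan.** The two-sample t-test (noncentral t) needs 85.03 per arm, rounded up to 86. Then 86 / (1 - 0.30) = 122.9, so 123 per arm and 246 in total. Power with 86 per arm is 90.3% at alpha 0.05 and 88.6% at alpha 0.04. With about 110 per arm (123 × 0.9 = 110.7), power at alpha 0.01 is 86.5%. All agree with the stated figures, so the sample size has no arithmetic error.

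**Step 2: dilution.** Assume that a share c of the PBT arm receives photons and has the photon-arm mean, with SD still 1. The expected difference is then 0.5 × (1 - c). For 90% power at alpha 0.05, solve for n per arm and divide by 0.7 for loss.

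| c | patients of 123 | difference | 5-year power, alpha 0.05 | 5-year power, alpha 0.04 | 2-year power, alpha 0.01 | total N for 90% at alpha 0.05 |
|---|---|---|---|---|---|---|
| 0 | 0 | 0.500 | 90.3% | 88.6% | 86.5% | 246 |
| 2% | about 2 | 0.490 | 89.2% | 87.3% | 84.9% | 256 |
| 5% | about 6 | 0.475 | 87.2% | 85.1% | 82.1% | 272 |
| 10% | about 12 | 0.450 | 83.5% | 81.0% | 76.9% | 300 |

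**Step 3: baseline adjustment.** Section 13.4 plans a model adjusted for baseline score. The protocol gives no correlation between baseline and 5-year score, so take r = 0.3 to 0.5 as an assumption. The residual SD is √(1 - r²), that is 0.954 to 0.866, and the standardised difference is 0.5 × (1 - c) / √(1 - r²). With 86 per arm and alpha 0.05:

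| c | r = 0 | r = 0.3 | r = 0.5 |
|---|---|---|---|
| 0 | 90.3% | 92.8% | 96.4% |
| 5% | 87.2% | 90.1% | 94.7% |
| 10% | 83.5% | 86.8% | 92.3% |

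At c = 5% the loss is 3.1 points unadjusted, 2.7 at r = 0.3 and 1.7 at r = 0.5. At c = 10% it is 6.8, 6.0 and 4.1 points. Adjustment shrinks the loss and raises the starting point, but it does not restore the diluted difference itself.

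**The case against.** The strongest reply is that consent already does this work. Patients hear the personal implications, normally have at least 24 hours to consider, talk to family and sign before randomisation (section 7.2). Someone who knows that six weeks away is impossible can decline, and the screening log in section 7.4 records caring duties, employment, ability to work remotely and reasons for declining. Section 1.5 commits the trial to supporting those who wish to take part. Accommodation is funded, patients may go home daily, and travel may be refundable. Photon fractions given to PBT patients are recorded (9.4, 11.2) and summarised (13.5), and the DMEC sees unblinded reports about yearly (14.1).

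Most of this stands, and it makes a large c less likely. It does not close the gap. Consent depends on how each of 18-25 sites explains the PBT course, it is not a checklist item on travel, and it cannot settle acceptance by a PBT centre. Recording non-receipt documents dilution without preventing it.

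Two stronger readings are tempting, and the documents support neither:

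- **That the acceptance step turns eligible patients away.** No section says that a trial-eligible patient can be refused PBT, or on what grounds. The detail sits in referral guidelines that are not shown, and the step may be administrative. PBT clinicians act as trial investigators (7.1), and patients whose severe co-morbidity makes them unsuitable for radiotherapy are already excluded from both arms (4.2).
- **That non-recipients will get photons locally.** Section 7.2 permits alternative treatment in either arm but names none. Photon treatment is the standard of care (1.3.1) and so a plausible fallback, but it remains an assumption of the calculation.

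**Conclusion.** The point holds as a cheap improvement. Attendance is an eligibility matter only for local follow-up, PBT referral and acceptance come after randomisation in one arm, and patients treated otherwise stay in the ITT comparison with no allowance in the sample size. ITT is still the right analysis. What can be avoided is randomising a patient who could not take up one of the two arms.

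The size is unknown because the protocol states no non-uptake rate. If non-recipients have the photon-arm mean, unadjusted 5-year power at alpha 0.05 falls from 90% by about 1 point at 2% non-uptake, 3 points at 5% and 7 points at 10%. The loss is smaller with the planned baseline adjustment. A reader might infer that the trial is underpowered or its sample size wrong. That does not follow: the stated figures reproduce, and even at 10% non-uptake unadjusted 5-year power stays above 80%.

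**What to change.** 1. Add to section 4.1 and the eligibility checklist: *Willing and able to receive either allocated treatment, including attending an NHS PBT centre on weekdays for the full course.*
2. State in section 3.1.2 that any PBT acceptance requirement beyond 4.1 and 4.2, if one exists, is checked for every patient before randomisation, so that the portal step after allocation is logistical only. If none exists, say so.

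**Cost.** One criterion, one sentence and one checklist line in an amendment. A few patients who could not have taken up PBT are screened out, which slightly lowers recruitment and narrows generalisability to patients able to travel for PBT. No dose, schedule or analysis changes.
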